#### 11.3. Informed Consent

The investigator shall verify that all potential patients for this registry are provided with a consent form describing this registry and sufficient information to make an informed decision about their participation.

The formal consent of a patient, using the EC-approved consent form must be obtained prior to a patient's entry in the registry.

The consent form will be signed

and personally dated by the patient and the person who conducted the informed consent discussion. The original signed informed consent form will be retained in the patient records. A copy of the informed consent document will be given to the patient for his or her records. Any significant, new information which emerges while the registry is in progress that may influence a patient's willingness to continue to take part in the registry will be provided to the patient.

The investigator shall verify that documentation of the acquisition of informed consent is recorded in each patient's records in accordance with applicable regulations.

Emergency contact details for reporting SAEs and serious adverse device effects will be listed in the EC-approved ICF.

#### 11.4. Independent Ethical Review

The investigator shall not enroll any patients prior to obtaining approval for the registry from a properly constituted independent EC.

The sponsor and / or designee will be responsible for submission of the IFU, protocol, draft ICF, eCRF (data requirements), and any other document required by the local EC for EC's written approval.

#### 11.5. Conflict of Interest

All investigators will follow applicable laws and regulations as well as the conflict of interest policies of their site and the reviewing EC.

11.6. Confidentiality

All patient records will be kept confidential to the extent provided by applicable laws and regulations. The registry monitors and other authorized representatives of the sponsor may inspect all documents and records required to be maintained by the investigator, including but not limited to medical records.

Such records may also be reviewed by the site's EC and other regulatory bodies. The investigator will inform the patients that their records will be reviewed.

11.7. Registry Discontinuation or Suspension

The entire registry may be suspended or prematurely terminated by Gore in the following cases:

- If new data become available which raises concern about the safety of the registry device, so that continuation of the registry might cause unacceptable risks to the patients.
- On recommendation by the CEC for any perceived safety concern based on clinical judgment, including, but not limited to, a higher than anticipated rate for any component of the safety endpoint, device failures resulting in AEs or unexpected SAEs.
- •

Registry participation of an individual registry site or an individual member of a registry site may be suspended or prematurely terminated by Gore in the following cases:

- If a principal investigator or EC responsible for the registry has withdrawn approval for any reason.
- If Gore monitoring or auditing identifies serious or repeated deviations on the part of the registry site or an individual investigator.
- If a site does not enroll any patients.

Procedures for suspension or premature termination of this registry are:

- If Gore or EC prematurely terminates the registry, all enrolled patients shall continue to be followed and treated as per standard of care at each site. Gore may request that patients are contacted or complete an office visit prior to registry termination.
- The investigator of each site or authorized designee shall promptly inform the enrolled patients.
- If the investigator receives notice that the EC approval has been withdrawn for any reason, the investigator shall notify Gore as soon as possible and preferably within 24 hours. Registry enrollment must immediately cease until such approval is reinstated.
- If Gore suspends or prematurely discontinues the registry, Gore shall inform the investigators, the ECs and the competent authority of the rationale and provide them with the relevant data supporting this decision.
- If the registry (or a registry site) is prematurely terminated a routine close out visit will be performed.

• If the investigator terminates or suspends a registry without prior agreement of the sponsor, the investigator should inform their institution where applicable, and the investigator / institution should promptly inform the sponsor and the EC, and should provide the sponsor and the EC a detailed written explanation of the termination or suspension.

The procedures of premature study termination of an individual patient (voluntary withdrawal or withdrawal of the patient by the investigator) are detailed in **Section 5.9** of the registry protocol.

Procedure for resuming the clinical investigation after temporary suspension:

- When Gore concludes an analysis of the reason(s) for the suspension, implements the necessary corrective actions, and decides to lift the temporary suspension, Gore shall obtain concurrence from the ECs and, where appropriate, the regulatory authority by providing the rationale and relevant data supporting this decision before registry enrollment resumes.
- When concurrence from ECs and, where appropriate, other regulatory authorities is obtained, Gore shall inform the investigators to resume the registry enrollment.
- If patients have been informed of the suspension, the principal investigator or authorized designee shall inform them of the reasons for resumption.

In addition, a final report to all reviewing ECs will be submitted within six months of completion, termination, or discontinuation. Sites that have enrolled a patient and have completed all patient follow-up requirements are asked to keep the clinical investigation active in order to receive the final study report.

## APPENDIX A

The development of registry inclusion and exclusion criteria, as described in **Table 4**, was performed in a manner to permit physicians to treat patients in a relatively free manner while also preserving basic safety and ensuring the protection of patients' rights.

Number	Text	Rationale
Inclusion #1	Age ≥ 18 years	Age of legal consent for adults
Inclusion #2	Signed informed consent form	An assurance that registry participant is a willing volunteer and aware of the risks / benefits of participation.
Inclusion #3	Endovascular indication for treatment based on treating physician's best medical judgment	Exposure to any endovascular procedure must be clinically warranted
Inclusion #4	Intend for no other stents to be placed in the same peripheral vessel(s) targeted for VBX Stent Graft placement	Consistent with purpose of registry
Inclusion #5	Willingness, in the opinion of the treating physician, to adhere to standard of care follow-up requirements	Registry participation needs to be of value in terms of follow-up data collection
Exclusion #1	Known hypersensitivity to heparin or a previous incident of Heparin-Induced Thrombocytopenia (HIT) type II	Contraindication to the VBX Stent Graft
Exclusion #2	Participation in concurrent research study or registry which may confound registry results, unless approved by Gore	To promote the ability to generate meaningful data on which statistical analyses can be made
Exclusion #3	Pregnant or breast-feeding female at time of informed consent signature	The use of the VBX Stent Graft in this population has not been tested and could present unnecessary risk to a fetus
Exclusion #4	Life expectancy < 12 months due to comorbidities	Consistent with the need for 12 month data as part of endpoint analysis
Exclusion #5	Use of the VBX Stent Graft is for the treatment of de novo iliac occlusive disease	Treatment of this particular pathology is not within scope and objective of this registry
Exclusion #6	Use of the VBX Stent Graft is for the treatment of aortic coarctations	Outside of the indicated use
Exclusion #7	Use of the VBX Stent Graft in the coronary, pulmonary, carotid, vertebral, isolated infrarenal aortic, or vena cava vessels	Outside of the indicated use

## Table 4. Inclusion / Exclusion Criteria Justification

## APPENDIX B

## PROTOCOL MODIFICATION SUMMARY

List of changes to VBX 17-04 Revision 6:

- Minor typographical and punctuation errors have been corrected throughout the protocol.
  - In addition, the following changes have been made to the protocol:

Section	Changes to Protocol	Rationale
Protocol - All sections	Extension of follow-up through five years. Corresponding sections, including flow chart and visit windows have been updated.	

List of changes to VBX 17-04 Revision 5:

• Minor typographical and punctuation errors have been corrected throughout the protocol.

Section	Changes to Protocol	Rationale
Protocol summary	Updated contact name for the Local representative	

• In addition, the following changes have been made to the protocol:

List of changes to VBX 17-04 Revision 4:

Minor typographical and punctuation errors have been corrected throughout the protocol.
 In addition, the following changes have been made to the protocol:

Section	Changes to Protocol	Rationale
Protocol - All sections	Total registry patient population increased to 280 patients. Corresponding sections, including Treatment Category caps, have been updated	
3.2.3. and protocol summary	Added "limb salvage" as secondary endpoint	
4.1.1. Table	Edited occlusive disease treatment indication example to "artery occlusive"	

5.3.	Edited language for clarity around consent after procedure	
9.1.	AE reporting will start from enrollment	
Table 1	Added definition of limb salvage	

List of changes to VBX 17-04 Revision 3:

Minor typographical and punctuation errors have been corrected throughout the protocol.
 In addition, the following changes have been made to the protocol:

Section	Changes to Protocol	Rationale
Protocol summary	Changed name and address of Local representative	
Protocol summary	Changed name and address of CRO	

List of changes in VBX 17-04 Revision 2:

- Revision 1 of the protocol was not distributed to sites
- Minor typographical and punctuation errors have been corrected throughout the protocol.

In addition, the following changes have been made to the protocol:

Section	Changes to Protocol	Rationale
4.2 Inclusion Criteria #3	Changed word Surgical with Endovascular	
APPENDIX A Inclusion Criteria #3 Text	Changed word Surgical with Endovascular	
APPENDIX A Inclusion Criteria #3 Rationale	Changed word Surgical with Endovascular	
Section 9.1.1. Adverse Event Relationship	Added category: Gore Accessory Use-related Any additional Gore devices that were used during the index procedure and / or reintervention caused or contributed to the AE

1.0 Introduction

This Statistical Analysis Plan (SAP) describes the statistical analyses planned to address the objectives of the VBX 17-04 registry is to collect post-market safety and performance data of the GORE[®] VIABAHN[®] VBX Balloon Expandable Endoprosthesis (VBX Stent Graft) in peripheral vessels in patients who require interventional treatment. This SAP summarizes the analyses that will be performed to determine the safety and effectiveness of the GORE[®] VIABAHN[®] VBX Balloon and outlines tables, figures, and listings that are included in reports for the VBX 17-04 clinical study.

2.0 Study Design Overview

Primary Objective(s)

The primary objective of the VBX 17-04 registry is to collect post-market safety and performance data of the GORE[®] VIABAHN[®] VBX Balloon Expandable Endoprosthesis (VBX Stent Graft) in peripheral vessels in patients who require interventional treatment

Design Summary

This registry utilizes a prospective, multicenter, non-randomized single-arm design to collect VBX Stent Graft clinical data in its use within the peripheral vasculature but outside of *de novo* iliac occlusive disease. Data will be representative of real-world, clinical use. Combined with data from long-term clinical investigations and reports from medical literature, real world clinical use data is integral for Gore to perform continuing assessments of its performance in addition to any long-term clinical investigations as well as reports in medical journals. To ensure that registry data is representative of real world use, the registry will employ broad inclusion / exclusion criteria to ensure its observational nature.

A maximum of 20 clinical registry sites (referred to as "sites" in the remainder of this document) in Europe will participate in this observational registry. Gore will maintain an updated list of all principal investigators, site names, and addresses. This list shall be kept separately from this protocol. From all enrolled subjects the first 280 implanted patients will be evaluated for the registry." No one site can contribute more than 35% of the total patient population (98 patients). There are no pathology-specific limitations at the registry or site level. The anticipated accrual rate is approximately 10 implanted patients per month for a total accrual period of approximately 28 months based upon the rapidity of site-start-up.Study Endpoints

Study Endpoints

2.1.1 Primary Endpoint(s)

The primary endpoint of the VBX 17-04 registry is a composite of the following events reported within 30 days of treatment.

- Procedural Success
- Freedom from VBX Stent Graft-related SAE

The first component, Procedural Success, describes the technical function of the VBX Stent Graft at the time of implant. The other component event, freedom from VBX Stent Graft-related Serious Adverse Event (SAE), is a description of short-term, device safety. Possible endpoint events will be identified from site reports and adjudicated by a Clinical Events Committee (CEC) for reporting eligibility.

2.1.2 Secondary Endpoint(s)

Selected events that are illustrative of the device's potential impact to a patient from a safety perspective, overall device function described as patency or device durability captured as device integrity are to be as the registry's secondary endpoints. Possible endpoint events will be identified from site reports with some secondary endpoints within scope of CEC adjudication.

The secondary endpoints for the VBX 17-04 registry are the following:

- VBX Stent Graft-related death within 30 days post-treatment
- Procedural-related death within 30 days post-treatment
- Procedural-related SAE within 30 days post-treatment
- VBX Stent Graft patency (primary, primary assisted, secondary) through 30 days post-treatment
- VBX Stent Graft patency (primary, primary assisted, secondary) through five years post-treatment
- VBX Stent Graft-related SAE through five years post-treatment
- VBX Stent Graft-related death through five years post-treatment
- Loss of device integrity through five years post-treatment
- Limb salvage through five years post-treatment

Protocol Term	Definition			
Procedural Success	Technical Success (successful access, delivery, accurate deployment, and withdrawal of catheters) with patent VBX Stent Graft at end of procedure			
Patency	 Primary - Uninterrupted patency with no procedures performed on or at the margins of the treated segment. Primary Assisted - Any procedure performed in the treated segment before thrombosis that might prevent eventual failure. Secondary - Any procedure that restores patency after thrombosis. 			
Loss of Device Integrity	 Defined as any of the following: Device damage that compromises device functionality (stent fractures, graft tears, cuts, holes, delamination) Transient (compression) or permanent stent-graft collapse (invagination) following complete device deployment, resulting in an overall reduction in the vessel luminal diameter 			
Limb Salvage	Freedom from Major Tissue Loss—extending above transmetatarsal level; functional foot no longer salvageable ²⁸			
Reintervention	An additional unanticipated interventional or surgical procedure (including conversion to open surgery), related to the device (including withdrawal of the delivery system) or procedure. Anticipated or unanticipated status will be determined at the discretion of the investigator			

Table 1. Protocol Definitions

	 This includes reintervention to the VBX device used during the Index procedure and not in non- VBX treatment areas 			
	A sealing failure at one of the attachment sites of the graft to the vessel wall providing arterial flow alongside the graft and into the perigraft space.			
Type I endoleak	Type Ia- Proximal attachment site			
	 Type lb- Distal attachment site 			
	 Type Ic- Inadequate seal at distal landing zone of branch vessel device 			
Type II endoleak	Retrograde flow through collateral vessels into the aneurysmal sac.			
Type III andelesk	Type IIIa- Arterial flow from module disconnection			
	Type IIIb- Arterial flow from fabric disruption			
Type IV endoleak	Arterial flow through porous fabric			

Statistical Hypotheses

No formal hypothesis will be tested in the study

Sample Size Assumptions

The assumptions that provided basis for the required sample size included Clinical success of 97.1% and freedom from device or procedure related SAEs to be 93.6%

Sample Size Calculations

Two hundred eighty (280) patients will be implanted with the VBX Stent Graft across multiple pathologies. The sample size of 280 patients was considered adequate to estimate study outcomes with reasonable precision and to have sufficient subjects enrolled within each indication. The sample size was determined by Gore to characterize broad device use across device indications. In combination with strategic selection of participating registry sites, this number should be sufficient to describe the study endpoints with less than 6% margin of error.

3.0 Study Treatment Arms

Test Arm Not applicable for registry

Control Arm(s) Not applicable for registry

4.0 Study Data Collection

To aid in registry reporting,

The Clinical Data Management System (CDMS) will be used to capture and maintain study data as per Clinical Data Management Plan describing the procedures for verification, validation, and security of the CDMS. The Clinical Data Management Plan will describe and document procedures regarding data management processes for this investigation.

a) Data Collection Methods

The CDMS will be the database of record for the protocol and subject to regulatory inspections and quality assurance review. All users will be trained to use the CDMS and will comply with study specific guidelines / instructions as well as applicable regulatory requirements.

Subject data will be collected using protocol-specific case report forms (CRF). Site staff will enter data directly into the CRF for transmission to the sponsor. The sites will be notified of any significant amendments to the CRFs.

b) Data Clarification and Correction

Once entered, data will be evaluated to confirm that it is complete, consistent, and logically sound. If changes to the data in the CDMS are required, all changes, reasons for changes, and persons making the changes will be captured in the CDMS's audit trail. Gore will perform periodic data reviews throughout the entire study. Procedures and documentation for regular and ongoing data review are described in the Clinical Data Management Plan.

c) CRF Completion Schedule

Entry of patient data into the EDC system cannot occur prior to the collection of the patient's informed consent to participate in the registry. All registry data is targeted to be entered into the appropriate CRF within two weeks of collection, however, data outside this window will not be considered a protocol deviation.

5.0 Clinical Event Committee

An independent Clinical Event Committee (CEC) will review safety- related, clinical events during the study to ensure the consistency of endpoints reported by the site. The VBX 17-04 CEC will be comprised of an interdisciplinary team of three members with pertinent expertise who are not directly involved in the conduct of the study.

The scope of the CEC activity includes the following:

- 1. General review and adjudication of Serious Adverse Events (SAEs) to include:
 - a. Adjudication on the SAE designation
 - b. Adjudication of the relationship of the SAE to the study device, procedure, or unrelated
- 2. Protocol Deviation review (as appropriate)
 - a. Due to the potential safety concern, protocol deviations associated with inclusion/exclusion criteria will be reviewed and the CEC will assess their risk for significant medical events that would not be expected from a subject that met all inclusion/exclusion criteria.

6.0 Statistical Analyses

No formal hypothesis will be tested for this registry. The registry is designed for broad data collection across multiple pathologies to aid in Gore's continuing assessment of risk with the real world use of the VBX Stent Graft. Due to the commercial nature of the device, the registry will not employ a pass / fail determination against pre-defined hypotheses but will instead measure observed performance of the entire registry population using a two-sided, exact binomial 95% confidence intervals for the primary outcomes.

i) Timing of Analyses

The final analysis will be performed when all subjects have completed their 5 years followup visit or have been withdrawn from the registry. Analyses will be performed as needed for annual reports. Analyses at any other time may be performed at the discretion of Gore.

ii) Analysis Populations

All enrolled patients meeting the inclusion / exclusion criteria and treated with the VBX Stent Graft will be included in the primary and secondary endpoint analyses.

iii) Pooling of Data

The VBX Stent Graft may be used in treatments that may differ by type of treatment (elective vs. emergent), patient risk (high vs. low / moderate) or role in treatment (primary repair vs. combinatorial repair). In each of these indications, the mechanism of introduction and device delivery will remain the same along with intended device function (lesion exclusion / vessel patency). The use of balloon-expandable stents are a well-known and practiced endovascular therapy that is not expected to differ between selected registry sites. As such, there is no concern in regards to pooling data from different European countries or sites together for analysis.

Gore may perform analyses to detect differences in device experience according to gender, age or pathology treated.

iv) Statistical Analysis of Primary Endpoint(s)

The two primary endpoints - procedural success and freedom from device-related SAE at 30 days will be presented descriptively as percentages with 95% confidence intervals. Subjects with missing information on the primary outcomes will not be included in the analysis.

v) Statistical Analysis of Secondary Endpoint(s)

Analysis of the secondary endpoints—device related death at 30 days, procedural related death at 30 days, procedural related SAE at 30 days, device patency at 30 days, in addition, device patency, device-related SAEs, device related deaths and loss of device integrity will be reported yearly as both yearly percentages and rates. Data will be presented descriptively with 95% confidence intervals, where appropriate. Subjects with missing information on these outcomes will not be included in the analysis.

vi) Analysis by Treatment Category

Individual device treatment indications will be categorized into larger groups "Treatment Categories" based upon either similar device function or purpose. Combining treatment indications into larger groups will permit the analysis of general treatment concepts where an analysis based upon an individual indication would not be feasible. Analyses of a Treatment Category will be performed descriptively with no pre-determined hypothesis.

vii) Analysis of Individual Treatment Indications

At the conclusion of enrollment, an evaluation of the distribution of device use across individual pathologies will be performed. If feasible, device experience by indication will be tabulated for descriptive analysis.

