### 3.2.2. Primary Endpoint

The primary endpoint of the VBX 17-04 registry is a composite of the following events reported within 30 days of treatment.

- Procedural Success
- Freedom from VBX Stent Graft-related Serious Adverse Event (SAE)

The first component, procedural success, describes the technical function of the VBX Stent Graft at the time of implant. The other component event, freedom from VBX Stent Graft-related SAE, is a description of short-term device safety. Possible endpoint events will be identified from site reports and adjudicated by a Clinical Events Committee (CEC) for reporting eligibility.

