10.3.4. Statistical Analysis of Primary Endpoint(s)

Tables of the primary endpoints procedural success and freedom from VBX Stent Graft-related SAEs at 30 days will be reported. Data will be presented descriptively with confidence intervals.

Missing data at the time of analysis will not be included in the denominator.

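### Both documents define one composite primary endpoint, but both visible primary-analysis sections report its two components as separate primary endpoints and give no composite estimate

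*SAP*

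**What the plan says.** **Definition.** Protocol 3.2.2 states: "The primary endpoint of the VBX 17-04 registry is a composite of the following events reported within 30 days of treatment". SAP 2.1.1 agrees that the primary endpoint "is a composite of the following events reported within 30 days of treatment". Both sections then describe procedural success and freedom from VBX Stent Graft-related SAE as its components, with possible events adjudicated by the Clinical Events Committee (CEC). The Protocol Summary also calls the endpoint a composite, but inserts the words *any of* before the list.

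**Analysis.** SAP 6.0 iv reads: "The two primary endpoints - procedural success and freedom from device-related SAE at 30 days will be presented descriptively as percentages", with 95% confidence intervals. Protocol 10.3.4 reads: "Tables of the primary endpoints procedural success and freedom from VBX Stent Graft-related SAEs at 30 days will be reported". The opening of SAP 6.0 promises two-sided "exact binomial 95% confidence intervals for the primary outcomes", in the plural.

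**Population and missing data.** SAP 6.0 ii says: "All enrolled patients meeting the inclusion / exclusion criteria and treated with the VBX Stent Graft will be included" in the primary and secondary analyses. Protocol 10.3.4 adds: "Missing data at the time of analysis will not be included in the denominator". SAP 6.0 iv adds: "Subjects with missing information on the primary outcomes will not be included in the analysis".

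**Sample size.** The SAP assumes 97.1% clinical success and 93.6% freedom from device- or procedure-related SAEs. It gives no composite rate. Both documents expect 280 implanted patients to give a margin of error below 6%.

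**The concern.** The endpoint that is defined is not the endpoint that is analysed. Followed as visible, the plan produces two component percentages and neither an estimate nor an interval for the quantity both documents call primary. Nor can a reader reconstruct it: a patient who fails both components counts once in the composite but once in each component table, and the overlap is not reported.

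What is at stake is which figure is presented as the primary result. In a descriptive registry that figure is the main product. As the text stands, the choice between a composite and two components that can only look as good or better could be made after the data are seen. The words *any of* in the Protocol Summary add a scoring doubt, since read literally one favourable component would be enough.

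**Working it through.** **1. The plan's own figure.** The stated margin is below 6% with n = 280. The normal-approximation half-width is 1.96 × √(p(1−p)/280):

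- p = 0.971: 1.97 points
- p = 0.936: 2.87 points
- p = 0.5 (worst case): 5.86 points

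The claim reproduces. With the exact interval the half-widths are 2.16 points (272/280), 3.06 points (262/280) and 6.01 points (140/280). Only the last exceeds 6, and it is far from the rates the SAP assumes.

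**2. What two percentages leave open.** Let a patients fail procedural success, b have a VBX Stent Graft-related SAE within 30 days, and c do both, with all n patients observed on both components.

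- Composite successes = n − (a + b − c).
- For the small failure counts considered here, c can be anything from 0 to min(a, b).
- Successes therefore run from n − (a + b) to n − max(a, b).
- Width of the range = min(a, b)/n.

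**3. Illustration.** The documents give no rate for either component as defined, so the SAP's assumed rates stand in for them. This is an assumption.

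- 0.971 × 280 = 271.9, so 272 successes and a = 8.
- 0.936 × 280 = 262.1, so 262 successes and b = 18.
- No overlap: 280 − 26 = 254, and 254/280 = 90.7%, exact 95% CI 86.7% to 93.8% (half-width 3.58 points).
- Full overlap: 280 − 18 = 262, and 262/280 = 93.6%, exact 95% CI 90.0% to 96.1% (half-width 3.06 points).
- Independent failures: 0.971 × 0.936 = 90.9%, close to the lower end.
- Width: 8/280 = 2.9 points.

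The exact limits are Clopper-Pearson: the 2.5% quantile of Beta(x, n−x+1) and the 97.5% quantile of Beta(x+1, n−x).

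**4. Sensitivity of the width to the assumed counts.**

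| Procedural failures | SAE failures | Width (points) |
|---|---|---|
| 8 | 18 | 8/280 = 2.9 |
| 4 | 18 | 4/280 = 1.4 |
| 8 | 3 | 3/280 = 1.1 |
| 1 | 18 | 1/280 = 0.4 |
| 0 | 18 | 0 |

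**5. Scoring with missing data.** Once a composite is computed, a patient known to have failed one component and missing the other must be classified. Dropping one such patient moves 254/280 = 90.71% to 254/279 = 91.04%, about 0.3 points. This arises only for the composite; for two separate percentages the stated rules can be applied outcome by outcome.

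**The case against.** The strongest reply is that the operational text is coherent as two outcomes. SAP 6.0 speaks of outcomes in the plural, both analysis sections list two, and the sample-size assumptions give two rates. On that reading the stray word is *composite*, and relabelling cures the problem without changing any analysis. This stands as an argument for a low rating and for offering relabelling as a remedy. It does not remove the conflict, because three definitions say composite and the two fuller ones explicitly call the items components.

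A reader might infer more than the documents support:

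- *That the composite was never planned.* Protocol 10.1 and SAP 9.0 show no text in this copy, and the SAP contents page lists analysis tables under 9.0. A composite table there cannot be excluded. It would still leave SAP 6.0 iv at odds with SAP 2.1.1.
- *That error rates or power suffer.* The SAP tests no hypothesis and has no pass/fail rule, so there is neither multiplicity nor power to lose.
- *That about 3 points is a bound.* It rests on borrowed rates. The 93.6% covers device- or procedure-related SAEs, whereas the endpoint counts only VBX Stent Graft-related ones, and Protocol 9.1.1 assigns each event a single primary relationship. Eighteen SAE failures is therefore probably too many.
- *That the denominator is part of the same contradiction.* The Protocol Summary, Protocol 3.1 and Protocol 5.5 read fairly consistently as implanted patients. How unsuccessful implants (Protocol 5.6.1) are handled is a separate question, as is the labelling of the SAP's assumed rates.

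**Conclusion.** The contradiction holds on the current text of both documents: one composite is defined, two separate primary endpoints are analysed, and no composite estimate is visible. The size is min(a, b)/280, which is 2.9 points under the stand-in rates and falls to zero if either component has no failures. That figure assumes complete data on both components and rates the SAP gives for differently named quantities, so it illustrates rather than predicts.

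The consequence is confined to which number is reported as primary. The sample size of 280 is unaffected, and at the illustrative rates the composite's exact half-width of 3.1 to 3.6 points is inside the 6% margin. Severity is minor.

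**What to change.** In SAP 6.0 iv and Protocol 10.3.4, add the proportion of patients in the stated analysis population who had both procedural success and no CEC-adjudicated VBX Stent Graft-related SAE through 30 days. Give it the exact binomial 95% interval already named in SAP 6.0 and show both components beside it. State that a patient known to have failed either component is a composite failure even if the other is missing, so that only patients whose composite status is unknown are left out. Delete *any of* from the primary endpoint in the Protocol Summary.

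If the sponsor instead intends two primary endpoints, restate the Protocol Summary, Protocol 3.2.2 and SAP 2.1.1 to say so.

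The first route costs some wording and one table row, with no new data and no change to 280. Its downside is that the headline composite will be no higher than either component. The second costs wording only, but gives up a single summary figure.
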